7.2 Subject demographics/other baseline characteristics

Patient demographic and baseline characteristic data will be collected on all subjects. The number of days between onset of COVID-19 symptoms and initiation of treatment will be recorded in all patients.

Investigators will have the discretion to record abnormal test findings on the medical history CRF whenever in their judgment, the test abnormality occurred prior to the informed consent signature.

7.2.1 Laboratory evaluations

Pre-treatment screening will include:

- Complete blood count (CBC), serum biochemical tests (including renal and liver function), troponin, NT-proBNP, albumin, total protein, coagulation profile, D-dimer, fibrinogen, LDH, CRP, serum ferritin, IL-6, quantiferon (optional), serum lipid panel (triglycerides), 2019-nCoV test.

On-treatment measurements (as noted in the schedule of activities):

- Complete blood count (CBC), serum biochemical tests (including renal and liver function), albumin, total protein, coagulation profile, D-dimer, LDH, CRP, serum ferritin, IL-6, 2019-nCoV test

7.2.2 Pregnancy assessments

All pre-menopausal women who are not surgically sterile will have a urine or serum pregnancy test performed at the screening visit, at the investigator's discretion. Pregnancy testing is not required for post-menopausal women.

8 Study discontinuation and completion

8.1 Discontinuation

8.1.1 Discontinuation of study treatment

Discontinuation of study treatment for a subject occurs when study treatment is stopped earlier than the protocol planned duration, and can be initiated by either the subject or the investigator.

The investigator must discontinue study treatment for a given subject if, he/she believes that continuation would negatively impact the subject's well-being. After study treatment discontinuation, patient should remain in the study, unless he/she withdraws consent (Section 9.1.2), preferably in writing.

Study treatment must be discontinued under the following circumstances
Mavri Covid 19 Protocol_3.0_ 25June2020

- Subject/guardian decision
- Pregnancy
- Use of prohibited treatment
- Any situation in which study participation might result in a safety risk to the subject
- Any laboratory abnormalities that in the judgment of the investigator prevents the subject from continuing study drug administration

If discontinuation of study treatment occurs, the investigator should make a reasonable effort to understand the primary reason for the subject's premature discontinuation of study treatment and record this information.

Subjects who discontinue study treatment or who decide they do not wish to participate in the study further should NOT be considered withdrawn from the study UNLESS they withdraw their consent. Where possible, they should return for the assessments indicated in the assessment schedule, **understanding that this may often not be possible with an ongoing COVID-19 pandemic, and therefore telehealth visits may be performed**. If they fail to return for these assessments for unknown reasons, every effort (e.g. telephone, e-mail, and letter) should be made to contact the subject/pre-designated contact as specified in the lost to follow-up section. This contact should preferably be done according to the study visit schedule.

If the subject cannot or is unwilling to attend any visit(s), the site staff should maintain regular telephone contact with the subject, or with a person pre-designated by the subject. This telephone contact should preferably be done according to the study visit schedule. Patient's vital status can also be verified by the study site upon contact with patient's primary care physician or other sources according to local rules and regulations.

After study treatment discontinuation, at a minimum, in abbreviated visits, the following data should be collected at clinic visits or via telephone/email contact:

- new/concomitant treatments
- adverse events/serious adverse events

8.1.1.1 Replacement policy

Subjects who are enrolled but not randomized will be replaced.

8.1.2 Withdrawal of informed consent

Subjects may voluntarily withdraw consent to participate in the study for any reason at any time. Withdrawal of consent occurs only when a subject:

- Does not want to participate in the study anymore

And

- Does not allow further collection of personal data

It is encouraged that patient provides withdrawal of consent in writing.

In this situation, the investigator should make a reasonable effort (e.g. telephone, e-mail, letter) to understand the primary reason for the subject's decision to withdraw his/her consent and

record this information. Patient's vital status can be verified upon contact with patient's primary care physician or other sources according to local rules and regulations.

Further attempts to contact the subject are not allowed unless safety findings require communicating or follow-up.

All efforts should be made to complete the assessments prior to study withdrawal. A final evaluation at the time of the subject's study withdrawal should be made as detailed in the assessment table.

Investigative sites will continue to keep and use collected study information (including any data resulting from the analysis of a subject's samples until the time of withdrawal) according to applicable law:

All biological samples not yet analyzed at the time of withdrawal may still be used for further testing/analysis in accordance with the terms of this protocol and of the informed consent form.

8.1.3 Lost to follow-up

For subjects whose status is unclear because they fail to appear for study visits without stating an intention to discontinue or withdraw, the investigator must show "due diligence" by documenting in the source documents steps taken to contact the subject, e.g. dates of telephone calls, registered letters, etc. A subject should not be considered as lost to follow-up until the end of the study while due diligence has been completed.

8.1.4 Early study termination by the sponsor

The study can be terminated by the Sponsor/Investigator at any time. Reasons for early termination:

- Unexpected, significant, or unacceptable safety risk to subjects enrolled in the study
- Decision based on recommendations from applicable board(s) after review of safety and efficacy data

In making the decision to terminate, the Sponsor/Investigator will always consider the subject welfare and safety. Should early termination be necessary, subjects must be seen as soon as possible and treated as a prematurely withdrawn subject. The investigator may be informed of additional procedures to be followed in order to ensure that adequate consideration is given to the protection of the subject's interests. The investigator or sponsor depending on the local regulation will be responsible for informing IRB of the early termination of the trial.

8.2 Study completion and post-study treatment

Study completion is defined as when the last subject finishes their Study Completion visit, and any repeat assessments associated with this visit have been documented and followed-up appropriately by the Investigator, or in the event of an early study termination decision, the date of that decision.

9 Safety monitoring and reporting

9.1 Definition of adverse events and reporting requirements

9.1.1 Adverse events

An adverse event (AE) is any untoward medical occurrence (e.g., any unfavorable and unintended sign [including abnormal laboratory findings], symptom or disease) in a subject or clinical investigation subject after providing written informed consent for participation in the study. Therefore, an AE may or may not be temporally or causally associated with the use of a medicinal (investigational) product.

The investigator has the responsibility for managing the safety of individual subject and identifying adverse events.

Qualified medical personnel will be readily available to advise on trial related medical questions or problems.

The occurrence of adverse events must be sought by non-directive questioning of the subject at each visit during the study. Adverse events also may be detected when they are volunteered by the subject during or between visits or through physical examination findings, laboratory test findings, or other assessments.

Adverse events must be recorded in the Adverse Events CRF under the signs, symptoms or diagnosis associated with them, accompanied by the following information (as far as possible) (if the event is serious refer to Section 10.1.2):

1. The severity grade:
 - mild: usually transient in nature and generally not interfering with normal activities
 - moderate: sufficiently discomforting to interfere with normal activities
 - severe: prevents normal activities
2. Its relationship to the study treatment. If the event is due to lack of efficacy or progression of underlying illness (i.e. progression of the study indication) the assessment of causality will usually be 'Not suspected'. The rationale for this guidance is that the symptoms of a lack of efficacy or progression of underlying illness are not caused by the trial drug, they happen in spite of its administration and/or both lack of efficacy and progression of underlying disease can only be evaluated meaningfully by an analysis of cohorts, not on a single subject
3. Its duration (start and end dates) or if the event is ongoing, an outcome of not recovered/not resolved must be reported.
4. Whether it constitutes a SAE (see Section 10.1.2 for definition of SAE) and which seriousness criteria have been met
5. Action taken regarding with study treatment.

All adverse events must be treated appropriately. Treatment may include one or more of the following:

- Dose not changed
- Drug interrupted/withdrawn
- Its outcome
 - a. not recovered/not resolved;
 - b. recovered/resolved;
 - c. recovering/resolving,
 - d. recovered/resolved with sequelae;
 - e. fatal; or unknown.

Conditions that were already present at the time of informed consent should be recorded in medical history of the subject.

Adverse events (including lab abnormalities that constitute AEs) should be described using a diagnosis whenever possible, rather than individual underlying signs and symptoms.

Adverse event monitoring should be continued for at least 60 days following the last dose of study treatment.

Once an adverse event is detected, it must be followed until its resolution or until it is judged to be permanent (e.g. Continuing at the end of the study), and assessment must be made at each visit (or more frequently, if necessary) of any changes in severity, the suspected relationship to the interventions required to treat it, and the outcome.

Information about adverse drug reactions for the investigational drug can be found in the Investigator Brochure (IB).

Abnormal laboratory values or test results constitute adverse events only if they fulfill at least one of the following criteria:

- they induce clinical signs or symptoms
- they are considered clinically significant
- they require therapy

Clinically significant abnormal laboratory values or test results must be identified through a review of values outside of normal ranges/clinically notable ranges, significant changes from baseline or the previous visit, or values, which are considered to be non-typical in subjects with the underlying disease.

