4.3 Risks and benefits

To date, there are no adverse events with a recognized causal relationship to exposure to mavrilimumab. However, there are a number of hypothetical risks that can be extrapolated from the mechanism of action. In particular, GM-CSF antagonism may interfere with immune response to infections. It is unknown how likely these effects are to occur, but their frequency may be lower with a one-time dose as compared to a longer duration to treat a chronic disease.

Frequent side effects:

- Nausea (approximately 1 in 10 subjects, self-limiting)
- Nasopharyngitis (approximately 1 in 10 subjects, self-limiting)
- Headache (approximately 1 in 10 subjects, self-limiting)

Rare but potentially life-threatening adverse reaction:

- Severe hypersensitivity reactions: While these have not been reported with Mavrilimumab, such reactions (including anaphylaxis, anaphylactoid reactions, cytokine release, and endotoxemia) have been observed after administration of other monoclonal antibodies. These reactions may be severe and may result in death.
- Leukopenia resulting in an increased risk of opportunistic infections. Mavrilimumab reduces the number of neutrophils. In some patients the reduction may be such to expose to additional (opportunistic) infection.

Additional potential side effects (of unknown frequency):

- Pulmonary alveolar proteinosis (PAP): studies have linked blockage of GM-CSF, the target of Mavrilimumab, with PAP. While the use of Mavrilimumab has not been

associated with the development of PAP in patients, a potential risk for this complication with Mavrilimumab use may exist.

- While the use of Mavrilimumab has not been associated with the development of cancer, drugs that modulate the immune response may increase the risk of cancer.
- Impaired response to vaccines. Drugs that reduce the immune response, like Mavrilimumab can impair the immune response to vaccine.
- Antibodies that inactivate the study drug thus losing its efficacy

In general, the risk to subjects in this trial may be minimized by compliance with the eligibility criteria and study procedures, close clinical monitoring, as well as periodic review of all safety data by an independent data monitoring committee (DMC).

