9.1.6 Data Monitoring Committee

This study will include a data monitoring committee (DMC) which will function independently of all other individuals associated with the conduct of this clinical trial, including the site investigators participating in the study. The DMC will assess at defined intervals the progress

of a clinical trial, safety data, and critical efficacy variables and recommend to the sponsor/investigator whether to continue, modify or terminate a trial.

Summary reports will be provided to a DMC after the first 5 subjects have been reviewed, after 15 subjects have been reviewed, and after every 10 subsequent patients.

Specific details regarding composition, responsibilities, data monitoring and meeting frequency, and documentation of DMC reports, minutes, and recommendations will be described in a separate charter that is established between the sponsor/investigator and the DMC.

Schedule of Safety Assessments:

Data Collection and Database management

Activity	Study Day													60	Unscheduled
	-3 to 0	0	1	2	3	4	5	6	7	14	21	28			
Vital signs	X	X	X		X		X		X	X	X	X		X	
Medications	X	X	X						X	X	X	X		X	
Respiratory parameters	X	X	X						X	X	X	X		X	
Hypersensitivity reaction			X	X	X	X	X	X	X						
Anaphylaxis reaction (defined according to Sampson's criteria, Sampson HA et al., J Allergy Clin Immunol. 2006 Feb;117(2):391-7		X	X	X											
Secondary Infections	X	X	X						X	X	X	X	X	X	
Hematology (CBC + diff: assessment for leukopenia, neutropenia, and thrombocytopenia)	X				X				X			X		X	
Coagulation (PT, PTT, INR)	X														
Chemistry (lytes, BUN, glucose, CR)	X				X				X			X		X	
Liver profile (AST, ALT, Alb, AlkP, Tbili, Dbili: assessment for drug-induced liver injury according to Hy's law)	X				X				X			X		X	
Adverse events	X	X	X	X	X	X	X	X	X	X	X	X	X	X	

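### The only adverse-event severity scale has no laboratory anchor, so symptom-free laboratory events of very different depth, such as neutropenia, can receive the same grade

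*Combined protocol and SAP*

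**What the plan says.** Section 9.1.1 requires a severity grade for each adverse event and offers three levels: "mild: usually transient in nature and generally not interfering with normal activities"; "moderate: sufficiently discomforting to interfere with normal activities"; and "severe: prevents normal activities". There is no higher level, and severity must be followed over time, with assessment at each visit "of any changes in severity".

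Abnormal laboratory findings fall within the definition of an adverse event. A laboratory value qualifies if it meets any one of three conditions. One is that it produces signs or symptoms. The other two do not require any: "they are considered clinically significant" and "they require therapy".

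Section 4.3 states that "Mavrilimumab reduces the number of neutrophils" and links this to opportunistic infection. The Schedule of Safety Assessments in section 9.1.6 lists blood counts with "assessment for leukopenia, neutropenia, and thrombocytopenia", and liver profiles with a Hy's law assessment.

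Section 10.3.1 plans tables of adverse events (each subject counted once per event type), tables of deaths and serious events, and patient listings. It specifies no table by severity and no summary of laboratory values.

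**The concern.** The scale describes how an event feels and what it stops a patient doing. A low neutrophil count or a raised transaminase may do neither until a complication follows. The protocol nevertheless admits such findings as adverse events and requires a grade for them. The grade would then carry little information about the laboratory risks that the protocol itself singles out.

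What is at stake is the usefulness of the severity data. The trial has 30 patients per arm and is meant to inform a Phase III trial. With so few patients, the depth of a cytopenia or a liver-enzyme rise tells the reader more than a count of patients with any such event.

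**Working it through.** No arithmetic decides this point. The check sets the relevant provisions side by side.

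1. **Can a symptom-free laboratory value need a grade?** Yes. Under section 9.1.1, clinical significance alone, or need for therapy alone, makes it an adverse event, and every adverse event is graded.

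2. **Which grade would it get?** Take a neutropenia without symptoms.
   - Severe requires that normal activities are prevented. Not met.
   - Moderate requires discomfort that interferes with activities. Not met.
   - Mild is met as to activities. Its other element, that the event is usually transient, is met only if the count recovers.

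   The event is therefore either mild or fits no definition cleanly. In neither case does the count enter the decision.

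3. **Illustration.** Suppose two symptom-free patients have counts of 1,400 and 300 per mm³, and both counts are recorded as adverse events. Against the 1,500 per mm³ limit in section 5.2, these are 1,400/1,500 = 93% and 300/1,500 = 20%. The written definitions give no ground for grading them differently. If one patient fell from the first value to the second without symptoms, the required assessment of change in severity would have nothing to register it with. The two counts are chosen for illustration; the protocol does not give them.

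4. **Is there a laboratory scale elsewhere?** Three candidates were checked.
   - Common Toxicity Criteria appears in the abbreviation list but is not applied anywhere in the text.
   - The neutrophil limit of 1,500 per mm³ in section 5.2 is an exclusion criterion.
   - Hy's law in the section 9.1.6 schedule is a case definition for liver injury. It does not grade severity and says nothing about blood counts.

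5. **Would the planned analysis show depth by another route?** Not as written. Section 10.3.1 covers events, deaths, serious events and listings, with no laboratory table by arm.

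6. **Will the values exist?** This is not assured. Footnote j to Table 7-1 calls for a differential at screening and only a blood count on later days. The haematology rows in Table 7-1 and in the section 9.1.6 schedule both name a count with differential and are marked at later visits. A blood count without a differential gives no neutrophil count. The footnotes to Table 7-1 also treat laboratory testing as standard of care, allow it to be omitted without a deviation, and end scheduled laboratory testing at discharge.

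**The case against.** The strongest reply is that the named risks have routes that do not depend on this scale. Seriousness is judged separately in section 9.1.2, which includes medically significant events and gives blood dyscrasias as an example. The section 9.1.6 schedule assesses cytopenias, liver injury and secondary infections directly. Section 10.3.1 plans no severity table, so no stated analysis fails. If laboratory values are collected, grades can be derived from them later. All of this stands, and it limits the weight of the point. It does not supply a laboratory anchor, and later derivation helps only if it is planned and post-baseline differentials exist.

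A reader might infer several stronger things that the documents do not support.

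- *That the scale cannot grade laboratory events, or makes every profound neutropenia mild.* A laboratory event with symptoms can be graded through them. The mild definition also mentions transience, so a persistent neutropenia is not mild by strict rule.
- *That every safety test in all 60 patients is affected.* Only values that meet one of the three conditions are graded. A count of 1,400 per mm³ might never be recorded as an event.
- *That the data monitoring committee would be misled.* Section 9.1.6 leaves monitoring details to a separate charter that is not among the documents.
- *That the scale cannot separate events in this population because illness already prevents normal activities.* All patients are inpatients at entry, with low saturation or on oxygen, so some compression is plausible. But the scale grades the event, not the patient's overall state, and the difficulty fades after discharge. This is a judgement and is not needed for the point.
- *That the listed abbreviation shows an intended scale left out by mistake.* It may simply be template residue.

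**Conclusion.** The point holds in a limited form. Section 9.1.1 creates symptom-free laboratory adverse events and grades them on a scale that takes no account of the laboratory value, and section 10.3.1 adds no laboratory summary to make up for it. Depth of neutropenia, a risk that the protocol attributes to the drug, could therefore be missing from both the severity grades and the planned tables by arm.

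The size cannot be put as a number, because the documents give no expected rate of laboratory adverse events. The scope is symptom-free laboratory abnormalities that an investigator judges clinically significant or treats. The conclusion assumes that investigators apply the definitions as written and that no laboratory scale is set in a document not supplied here. Sample size and alpha are not touched. This is a cheap improvement to the safety data and does not threaten the trial's main conclusion.

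**What to change.** - **Section 9.1.1:** grade laboratory adverse events by a named published scale with numeric cut-offs, for example CTCAE, with the version fixed before unblinding. The present three-level scale can stay for symptomatic events if the sponsor prefers. Either give the Common Toxicity Criteria abbreviation a use or delete it.
- **Section 10.3.1:** add, by arm, the worst post-baseline grade derived by program and a baseline-to-worst shift table for neutrophils, platelets, ALT/AST and bilirubin. State how many patients have post-baseline values for each test, because testing follows standard of care and stops at discharge.
- **Table 7-1 and the section 9.1.6 schedule:** reconcile footnote j with the haematology rows, so that it is clear whether post-baseline neutrophil counts will be available.

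The cost is small: wording in two sections and a footnote, a change to the eCRF severity field, some programming and brief site training. If the reconciliation confirms later differentials, the values for the new tables come from tests already scheduled.
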